23.2 Retention of human biospecimens

Storage and disposition of samples analysed at local laboratories will be performed according to local laboratory procedures.

Antibody samples (samples for binding antibodies and inhibitors) will be stored until drug approval by Food and Drug Administration (FDA) and/or European Medicines Agency (EMA).

Protocol v 1 | 107 of 114 Protocol Date: 04 November 2013 | **Novo Nordisk**

 Trial ID: NN7088-3908
 Version:
 1.0

 UTN: U1111-1148-1897
 Status:
 Final

 EudraCT No.: 2013-004025-88
 Page:
 108 of 114

All remaining blood samples will be stored until the trial has been evaluated by appropriate authorities or until the project terminates, but no longer than 15 years from end of trial. As new biomarkers related to the disease and/or safety, efficacy, or mechanism of action of N8-GP may evolve during the conduct of the trial, the analyses of the stored biospecimens may also include biomarkers that are unknown at present or have not been included in the scientific hypotheses at initiation of the trial. The samples will be stored at Novo Nordisk or a Novo Nordisk designated referral bio-repository with access to the samples. Samples might be transferred to other countries, if not prohibited by local regulations. The patient's identity will remain confidential and samples will only be marked and identified by a unique sample ID. No direct identification of the patient will be stored together with the samples. The analyses will not have any medical consequences for the patients or their relatives. Only Novo Nordisk staff and bio-repository personnel (if applicable) will have access to the stored bio specimens.

Protocol v 1 | 108 of 114

Protocol Trial ID: NN7088-3908

UTN: U1111-1148-1897 EudraCT No.: 2013-004025-88

Date: Version: Status: Page:

04 November 2013 | **Novo Nordisk** 1.0 Final 109 of 114

24 Institutional Review Boards/Independent Ethics Committees and regulatory authorities

IRB/IEC:

Written approval or favourable opinion must be obtained from IRB/IEC prior to commencement of the trial.

During the trial, the investigator or sponsor, as applicable, must promptly report the following to the IRB/IEC, in accordance with local requirements: updates to IB, unexpected SAEs where a causal relationship cannot be ruled out, protocol amendments according to local requirements, deviations to the protocol implemented to eliminate immediate hazards to the patients, new information that may affect adversely the safety of the patients or the conduct of the trial (including new risk/benefit analysis in case it will have an impact on the planned follow-up of the patients), annually written summaries of the trial status, and other documents as required by the local IRB/IEC.

Protocol amendments must not be implemented before approval or favourable opinion according to local regulations, unless necessary to eliminate immediate hazards to the patients.

The investigator must maintain an accurate and complete record of all submissions made to the IRB/IEC. The records should be filed in the investigator's trial file and copies must be sent to Novo Nordisk.

Regulatory Authorities:

Regulatory authorities will receive the clinical trial application (CTA), protocol amendments, reports on SAEs, and the CTR according to national requirements.

Protocol v 1 109 of 114 Protocol Date: 04 November 2013 Novo Nordisk
Trial ID: NN7088-3908 Version: 1.0

25 Indemnity statement

Novo Nordisk carries product liability for its products, and liability as assumed under the special laws, acts and/or guidelines for conducting clinical trials in any country, unless others have shown negligence.

Novo Nordisk assumes no liability in the event of negligence, or any other liability of the sites or investigators conducting the trial, or by persons for whom the said site or investigator are responsible.

Novo Nordisk accepts liability in accordance with:

Only applicable for Argentina: Novo Nordisk Pharma Argentina S.A. has contracted insurance (policy reference number 87828 and its respective updates) with the company Sancor Cooperativa de Seguros LTDA. Domiciled in [name]. [contact].

Only applicable for Australia: Medicines Australia Guidelines for Compensation for Injury Resulting From Participation in a Company-sponsored Clinical Trial. Version 160104B dated 16 January 2004.

Only applicable for Austria: Arzneimittelgesetz (BGBI. Nr. 185/1983) last amended with BGBl. I Nr. 48/2013

16.1.01 Protocol Attachment

Protocol Attachment I is located in the Trial Master File.

If applicable, Protocol Attachment II is also located in the Trial Master File.

Content: Global key staff and Country key staff.

Log of Protocol Amendments Trial ID: NN7088-3908

UTN: U1111-1148-1897 EudraCT No.: 2013-004025-88

Date: Version:

08 February 2022 | Status: 2.0 | Page:

Final | Novo Nordisk

Log of Protocol Amendments

Trial ID:

Protocol amendment no	Date	Final, Version	Country(ies) and/or trial site(s) affected	Brief content
1	NA	NA	Portugal	Protocol amendment no 1 was dedicated to Portugal but never finalised. Due to SOP requirements the countries now have their own logs and this log will only cover global amendments
2	20-Mar-2015	2.0	All	(Final Version 1.0 never shared) Detailed information on Major surgery and ITI, extended trial timelines
3	01-Nov-2016	1.0	All	Amendment 3 includes a new secondary endpoint to assess the ITI treatment outcome and monitoring of antibody development against Host Cell Protein (HCP).
4	14-Jun-2018	1.0	Israel	Protocol Amendment 4 is for Israel seeking permission to obtain the F8 genotype.
5	13-Jun-2019	1.0	All	Interim analysis when approximately 45 patients have reached 50 exposure days, and administrative changes
6	21-jun-2019	1.0	Israel	Protocol amendment 6 for Israel for obtaining informed consent from withdrawn patients to provide genotype results

VV-TMF-1130009|2.0|NN7088 -3908

Log of Protocol Am Trial ID: NN7088-3		UTN: U1111-1148-1 EudraCT No.: 2013-0		Date: Version:	08 February 2022 2.0	Status: Page:	Final 2 of 2	Novo Nordisk
7	02-jul-2019	1.0	Jap	pan	regulatory cate updated in acc This is m	endment 7 for J egory of this clin cordance with Ja andatory before ceting approval of	nical trial shoul panese regulat NNPL obtains	ld be ions.
8	15-Jun-2020	1.0	A	All	between 5 (rather that completing defined tri	uitment of trial 10 to 100 patients in the protocol agg), but maintain al end date 13 N IgG + additionates have been in	s completing, greed 100 patie the protocol November 2021 al IgM antibody	ents .

Protocol Amendment Trial ID: NN7088-3908 UTN: U1111-1148-1897

EudraCT No.: 2013-004025-88

CONFIDENTIAL

Date: Version: Status: Page: 30 July 2014 | **Novo Nordisk**0.1 | Final | 1 of 5

1 0

Protocol Amendment

no 1.0 to Protocol, final version 1.0 dated 04 November 2013

Trial ID: NN7088-3908

An open-label single arm multicentre non-controlled phase 3a trial investigating safety and efficacy of N8-GP in prophylaxis and treatment of bleeding episodes in previous untreated paediatric patients with severe haemophilia A

Trial phase: 3a

Applicable to all countries

Amendment originator:

, International Trial Manager

Department: Haemophilia, Clinical Operations 2

This confidential document is the property of Novo Nordisk. No unpublished information contained herein may be disclosed without prior written approval from Novo Nordisk. Access to this document must be restricted to relevant parties.

CONFIDENTIAL

 Date:
 20 March 2015
 Novo Nordisk

 Version:
 2.0

 Status:
 Final

 Page:
 2 of 41

Table of Contents

	P	Page
Tal	ble of Contents	2
Tal	ble of Figures	2
Tal	ble of Tables	2
1	Introduction including rationale for the protocol amendment	3
2	Changes	6

Table of Figures

No table of figures entries found.

Page

Table of Tables

Page

No table of figures entries found.

CONFIDENTIAL

 Date:
 20 March 2015
 Novo Nordisk

 Version:
 2.0
 Status:
 Final

 Page:
 3 of 41
 Final

1 Introduction including rationale for the protocol amendment

Rationale for amendment

Below list is the items that have been changed and the rationales for the amendment. The reason for the creating the amendment now is the availability of results from the pathfinderTM2 (NN7088-3859), pathfinderTM3 (NN7088-3860) and pathfinderTM5 (NN7088-3885).

- 1. Major surgeries has been allowed after having completed the pathfinder™3 surgery trial. (section 5.3.5, 8.7)
 - a. Recommendations for doses has been added (section 5.3.5, 8.7)
 - b. Details on definition of data sampling has been updated and data collection from minor and major surgery aligned (section 5.3.5, 8.1.10, 8.7)
 - c. Haemostatic response for surgery 4-point scale added (section 8.6.1, 8.7.1)
- 2. ITI recommendations and requirements have been updates after new data available from pathfinderTM2 pivotal trial, pathfinderTM3 surgery trial and pathfinderTM5 paediatric trial to support the ITI recommendations. (section 5.3.6)
 - a. Dose recommendations added (section 5.3.6, 8.1.11)
 - b. Detailing of recommendations for low titre inhibitor patients added (section 5.3.6, 5.5, 6.4, 6.6.3)
 - c. How to evaluate the ITI treatment before returning to prophylaxis added (section 5.3.6, 6.4, 6.6.3, 8.1.11, 8.4.2.2, 16)
 - d. ITI doses will count as overall number of doses (section 5.1)
- 3. Prolonged recruitment period and prolonged trial. Prolongation is due to postponed submission of the application for market approval of N8-GP (section 5.3, 7, 8.1)
- 4. Updated text on when trial could start as needed data is available at this point (section 3.1.3, 5.1, 5.3, 8.7)
- 5. Addition of mandatory inhibitor test before treatment including addition of a withdrawal criterion if positive at visit 1 before first dosing. This has been added because of the risk of developing inhibitors after receipt of maximum 5 doses of blood components. (section 2, 6.2, 6.4, 8.1)
- 6. Precised when safety committee should meet instead of having an interval for the meeting (section 11.6.2, 16.6)
- 7. PK time points have been changed based on the need experienced from the first patients enrolled in the trial. (section 8.4.2.2)
- 8. Allergic reaction sampling updated with 2 new tests, as found relevant based on the experience form the first patients enrolled in the trial. (section 8.4.2.7)
- 9. All wash out periods before pre-dose blood sampling has been aligned to be 72 hours instead of either 72hour or 4 days. This changed in implemented because of new information from the pathfinderTM5 paediatric trial. (section 8.4.2.2)

- 10. Analyses of binding antibodies and PEG antibodies have been changed to not only being analysed at the end of the trial to also being analysed when considered relevant, based on experience from first patients in the trial. (section 8.4.2.2)
- 11. Added a window for sampling of blood at visits to allow more flexibility for the patients and sites (section 8.1, 8.4)
- 12. Clarified inclusion criterion 4 to be covering only FVIII purified product and not all faction products (section 1, 5.3, 6.2)
- 13. Added cardio vascular to physical examination (section 8.3.2)
- 14. Elaborated on drug reconstitution and solvent supplies (section 9)
- 15. Added informed consent can be signed before first visit (section 8.1)
- 16. Clarified dosing regimen text and visit windows (5.3, 8.1,
- 17. Reminder of monitoring of expiry of solvent, injection kits, and reference standard based on experience from pathfinderTM and guardianTM programmes. (section 8.1, 8.8.4, 9.4)
- 18. Added information that the vein used for drug infusion can be used for blood sampling half an hour after the infusion to ease the problematic blood draw from infants (section 8.4)
- 19. Changed the form of writing visit windows in table 2-1 after feedback of being difficult to understand (section 2)
- 20. Elaborated figure 8-1 to be more precise for visits during the pre-prophylaxis period. (Section 8.1)
- 21. Added that if according to local law a caregiver can take over some of a parent(s)/LAR(s) task to allow more flexibility for patients (section 8.1)
- 22. Added reminders to the visit 15-X to help site following the trial requirements (section 8.1.3)
- 23. Requirement for site to be able to analyse FVIII activity and inhibitor samples locally to ensure immediate action if needed for the patient's safety. This has been added based from experience from the initiation of the trial (section 8.4.1.1)
- 24. Added extra samples to be taken together with the confirmatory inhibitor test to ensure a positive test is not a false positive and to ensure sufficient knowledge of the inhibitor (section 8.4.2.2)
- 25. Added that monitoring visit intervals can be prolonged when site only have patients attending visits every 24 weeks, but monitor needs to ensure contact to site at least every 12 weeks (section 13)
- 26. Added that the e-learning of the protocol is mandatory for Investigator if investigator has not attended the investigators meetings (section 21)
- 27. Deleted specific text for Japan upon request from Japan (section 23.1)
- 28. Added required text for Portugal upon amendment 1 (section 25)
- 29. Clarified table 2-1 elements (section 2)
- 30. Updated total blood sampling volume after having finalised lab set-up (section 8.4.3)
- 31. Clarified where to enter data in eCRF and eDiary (section 8.1, 8.2, 8.8)
- 32. Clarified location to align with rest of protocol (section 5.3)
- 33. Deleted repetitive text (section 3.2)

Protocol Amendment		Date:	20 March 2015	Novo Nordisk
Trial ID: NN7088-3908	CONFIDENTIAL	Version:	2.0	
UTN: U1111-1148-1897	CONFIDENTIAL	Status:	Final	
EudraCT No.: 2013-004025-88		Page:	5 of 41	

34. Added required elements from new protocol template. It was decided not to change to the new protocol template as this would change the protocol too much for sites convenience, but all relevant elements from the new protocol template has been added to the protocol. (section 3, 4, 5, 6, 8, 16, 17, 20, 21, 22, 23, 24)

Corrected abbreviation order, spelling, grammar and clarifications, text formatting, and incorrect section references.

In this protocol amendment:

- Any new text is written *in italics*.
- Any text deleted from the protocol is written using strike through.

20 March 2015 | Novo Nordisk Protocol Amendment Date: Trial ID: NN7088-3908 CONFIDENTIAL

UTN: U1111-1148-1897 EudraCT No.: 2013-004025-88

Version: 2.0 Status: Final Page: 6 of 41

Changes 2

General over whole protocol

- IV/WRS to IWRS
- Bleed to Bleeding episode
- Spelling corrections and grammatical corrections and corrected section references have not been listed below

List of Abbreviations

CRPC-reactive protein

APTT activated partial thromboplastin time

1 Summary

Trial population: Inclusion criteria

• No prior use of purified factor VIII containing clotting factor products (5 previous exposure days to blood components is acceptable)

2 Flow Chart

Table 2-1

Table 2-1											
Visit number	0 ¹	1 ¹	2	3	4-6	7-8	9	10-13	14 ¹⁸	15-X ¹⁹	EOT
Time of visit (ED(s)) ²	0	1	2	5	10, 15, 20 ³	30,40	50	60, 70, 80, 90	100	NA	
Visit interval (ED(s)) ²		0	0	3±1	5 ±2	10 ±2	10 +2	10 ±2	10 +2	24w±4w	
Adverse events ⁵	Х	Х	Χ	Х	Х	Х	Х	Х	Х	Х	Χ
				•							
Vital signs ⁷	Х	X ⁷					Х		Х		Х
 											
FVIII activity – recovery (30 min post-dose)		Х		х	х	Х	х	х	х	Х	
,											
FVIII inhibitor test9		X ¹⁸		Х	Х	Χ	Х	Х	Х	Х	Х
HIV 1 and 2 antibodies	(X) 10										
F8 + HLA genotype testing	(X) ¹²	(X) ¹²									
eDiary training		X ¹⁴	X ¹⁴	X ¹⁴	X ¹⁴	X ¹⁴	X ¹⁴	X ¹⁴	X ¹⁴	X ¹⁴	

T J	Protocol Amendment Trial ID: NN7088-3908 UTN: U1111-1148-1897 EudraCT No.: 2013-004025-88				CONFIDENTIAL			Date: Version: Status: Page:		20	20 March 2015 2.0 Final 7 of 41		
c p	Compliance check of eDiary data, protocol requirements, and		X	X	×	X	X	X	X	X	×	X	

Table 2-2

used drug and bleeding episode evaluation

1 abic	
3	If not already on prophylaxis, all patients must initiate prophylaxis treatment no later than at V6 or shortly after at ED 20. Pre-prophylaxis is only allowed for children below the age of 24 months or up to V6, whatever comes first. Visits at 10EDs±2EDs, 15EDs±2EDs, 20EDs±2EDs must be performed even the window allows 2 visits to be 2 EDs aside (e,g, ED12 and ED13)
5	After Informed consent has been obtained all Adverse Events if associated with trial related activities must be reported in the eCRF
7	Vital signs should be measured prior to dosing at all screening V1, V9, and at V14 and at EOT. In addition vital signs should also be measured 30±10minutes after the first injection with N8-GP at V1.
9	Blood samples must be collected prior to dosing at dosing visits. Please check that the required washout period has been met for inhibitor testing, see section 8.1.1.3 Before any surgeries are performed an inhibitor test must be taken if this test is more than 30 days
12	F8 and HLA genotype sample is only allowed upon patient's parent(s)/LAR(s) signing the consent for genotyping and should only be done if not already documented in patient's medical record. The sample can be collected at any visit between V0 and V89, taking the limitation of the allowed blood sampling volume into account. Genotype is not applicable for Israel.
18	In case V14 will be the EOT visit, the procedures for the EOT visit should be followed-Inhibitor sample at visit 1 before dosing is mandatory
19	V15 to VX will be performed every 24 weeks EDs ± 4 weeks EDs until the End of Trial

3 Background information and rationale for the trial

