 Novo Nordisk

Table 2–2 Flow chart explanatory descriptions

Footer	Description
1	V0 and V1 can be combined to one visit, if the patient fulfils the in- and exclusion criteria
2	When the patient has commenced prophylaxis, visits can for practical purposes be planned according to the predicted number of EDs based on the patient's prophylaxis regimen. A visit does not need to be re-scheduled even if the actual EDs between visits turn out higher or lower due to treatment of bleeding episodes during the home treatment period.
3	If not already on prophylaxis, all patients must initiate prophylaxis treatment no later than at V6. Pre-prophylaxis is only allowed for children below the age of 24 months or up to V6, whatever comes first. Visits at 10EDs±2EDs, 15EDs±2EDs, 20EDs±2EDs must be performed even the window allows 2 visits to be 2 EDs aside (eg ED12 and ED13)
4	Any patient above the age of 3 years should sign a child assent form, if capable, and if required by local requirements. This can be performed on a separate day. As this is a long term trial the investigator should check the progressing maturation of the child and his ability to assent throughout the trial.
5	After Informed consent has been obtained all Adverse Events must reported in the eCRF
6	The frequency of body weight measurements should follow local practice, but should at least be measured every 10 weeks in children ≥ 3 years of age and within a timeframe of 6 weeks in children ≤ 3 years of age. Please refer to Section $8.3.1$
7	Vital signs should be measured prior to dosing at all screening, V1, V9, V14 and EOT. In addition vital signs should also be measured 30±10minutes after the first injection with N8-GP at V1.
8	FVIII activity should only be measured at V0 if diagnosis of haemophilia A (FVIII<1%) has not been documented in the patients' medical record. FVIII activity at V0 can either be measured at local or central laboratory depending on the urgency of receiving the result i.e. in case V0 and V1 are combined
9	Blood samples must be collected prior to dosing at dosing visits. Please check that the required washout period has been met for inhibitor testing, see section 8.1.1.3

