4.2.2 Secondary Endpoint

- Frequency of Adverse events (AEs) including serious AEs and Medical Events of Special Interest (MESI).*
- Incidence of confirmed high titre inhibitors (defined as inhibitor titre > 5BU)*
- Number of breakthrough bleeding episodes during prophylaxis with N8-GP (annualised bleeding rate).*
- Haemostatic effect of N8-GP in treatment of bleeding episodes, assessed by a predefined 4-point haemostatic response scale ("excellent", "good", "moderate" and "none").*
- Consumption of N8-GP for prophylaxis (number of injections and U/Kg per month and per year)
- Consumption of N8-GP for treatment of bleeding episodes (number of injections and U/Kg required per bleeding episode)
- Total consumption of N8-GP per patient (prevention and treatment of bleeding episodes) per month and annualised value

Protocol v 1 | 24 of 114

^{*}Key supportive secondary endpoint prospectively selected for posting on clinicaltrials.gov

UTN: U1111-1148-1897 EudraCT No.: 2013-004025-88 Version: 1.0
Status: Final
Page: 25 of 114

5 Trial design

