11.2 Reporting of adverse events

All events meeting the definition of an AE must be collected and reported. This includes events from the first trial-related activity after the patient's parent(s)/LAR(s) has signed the informed

Protocol v 1 | 78 of 114

^{*30%} decrease from that person's baseline

EudraCT No.: 2013-004025-88

 Protocol
 Date:
 04 November 2013
 Novo Nordisk

 Trial ID: NN7088-3908
 Version:
 1.0

 UTN: U1111-1148-1897
 Status:
 Final

Page:

79 of 114

consent until the end of trial visit. The events must be recorded in the applicable CRF forms in a timely manner. See timelines below and Figure 11–1.

AEs between consent and first dosing should only be reported if associated with trial related activities.

During each contact with the trial site staff (trial site visits and telephone contacts), the patient and/or patient's parent(s)/LAR(s) must be asked about AEs and technical complaints, e.g. "Have you experienced any problems since the last contact?"

All AEs, either observed by the investigator or reported by the patient, must be reported by the investigator and evaluated. Novo Nordisk assessment of expectedness is performed according to the following reference documents: investigator's brochure, ⁵ N8-GP, current version and any updates thereto.

All AEs must be recorded by the investigator on an AE form. The investigator should report the diagnosis, if available. If no diagnosis is available, the investigator should record each sign and symptom as an individual AE using separate AE forms.

For each SAE and MESI an electronic Safety Information Form (eSIF) should be completed in addition to the AE form in the eCRF, see Figure 11–1. If several symptoms or diagnoses occur as part of the same clinical picture, one eSIF may be used to describe all the SAEs. All concerned AE numbers must be included in the AE number field on the eSIF.

MESIs, regardless of seriousness, must be reported using both the AE form and the safety information form. For MESIs of allergic aetiology, the hypersensitivity questionnaire must be completed.

The AE form for a non-serious AE should be signed when the event is resolved or at the end of the trial.

Timelines for initial reporting of AEs:

The investigator must complete the following forms in the eCRF within the specified timelines:

• **SAEs**: The AE form **within 24 hours** and the safety information form **within 5 calendar** days of the investigator's first knowledge of the SAE.

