11.2 Reporting of adverse events

. . .

All AEs, either observed by the investigator or reported by the patient, must be reported by the investigator and evaluated. Novo Nordisk assessment of expectedness is performed according to the following reference documents: investigator's brochure, N8-GP, current version and any updates thereto.

For Japan only: If obtaining marketing approval in Japan, sponsor's assessment of expectedness is done according to the package insert of the commercial products in Japan.

| 3 of 3

...

Date: Version: Status: Page:

15 June 2020 | Novo Nordisk Final 1 of 10

Protocol Amendment

no 8

to Protocol, version 1.0 dated 04 November 2013

Final Protocol version 1.0 (04-Nov-2013) including:

Amendment no. 1, version 0.1, Portugal (30-Jul-2014)

Amendment no. 2, version 2.0 (20-Mar-2015)

Amendment no. 3, version 1.0 (01-Nov-2016)

Amendment no. 4, version 1.0, Israel (14-Jun-2018)

Amendment no. 5, version 1.0 (13-Jun-2019)

Amendment no. 6, version 1.0, Israel (21-Jun-2019)

Amendment no. 7, version 1.0, Japan (02-Jul-2019)

Trial ID: NN7088-3908

Safety and Efficacy of turoctocog alfa pegol (N8-GP) in Previously Untreated Patients with Haemophilia A

> Trial phase: 3a Applicable to all countries

This confidential document is the property of Novo Nordisk. No unpublished information contained herein may be disclosed without prior written approval from Novo Nordisk. Access to this document must be restricted to relevant parties.

Table of Contents

1	Introduction including rationale for the protocol amendment	3
2	Changes	.4

Date: Version: Status: Page:

15 June 2020 | Novo Nordisk Final 3 of 10

1 Introduction including rationale for the protocol amendment

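### Amendment 2's footer 5 to Table 2-2 restricts adverse event reporting after consent without the first-dosing limit that section 11.2 sets, so the flow chart and section 11.2 conflict for the treatment period

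*Combined protocol and SAP*

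**What the plan says.** In protocol version 1.0, footer 5 of Table 2-2 put no restriction on reporting once consent was given: "After Informed consent has been obtained all Adverse Events must reported in the eCRF". Amendment 2 (20 March 2015) lists footer 5 among its flow-chart changes, and it now reads "After Informed consent has been obtained all Adverse Events if associated with trial related activities must be reported in the eCRF". The footer marker sits on the AE row of Table 2-1, which carries an X at every visit column from V0 to EOT.

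Section 11.2 states the general rule, "All events meeting the definition of an AE must be collected and reported", for the period from the first trial-related activity after consent until the end of trial visit. It then makes one exception: "AEs between consent and first dosing should only be reported if associated with trial related activities".

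Section 4.2.2 lists "Frequency of Adverse events (AEs) including serious AEs and Medical Events of Special Interest (MESI") as the first secondary endpoint and flags it as a key supportive one. Section 16.4.2.5 summarises AEs as treatment-emergent, meaning those that occur after dosing with trial product, and cross-classifies them by severity and causal relation.

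**The concern.** The amended footer takes over the restriction from section 11.2 but not the period to which section 11.2 confines it. Read literally, it carries a pre-dose rule through the whole treatment period. Section 6.2 (criterion 1) defines trial-related activities as procedures carried out as part of the trial. An intercurrent infection in a treated child need not be associated with any such procedure, so a site could reasonably conclude from footer 5 that no entry is needed.

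At stake is the completeness of the treatment-emergent AE summaries, because the conflict falls on the post-dose period that they cover. The trial has one arm and no comparator (section 5.1), so any under-recording passes straight into the reported frequencies. If sites differ in which text they follow, their counts also differ for a reason unrelated to the product.

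**Working it through.** The plan gives no AE rate and no share of AEs associated with trial activities, so there is no plan figure to reproduce. The check is a comparison of texts.

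**Step 1. What each text requires**

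| Text | Consent to first dosing | First dosing to EOT |
|---|---|---|
| Footer 5, version 1.0 | All AEs | All AEs |
| Footer 5, Amendment 2 | Only if associated with trial activities | Only if associated with trial activities |
| Section 11.2 | Only if associated with trial activities | All AEs |

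In version 1.0 the footer and section 11.2 disagreed before dosing. After Amendment 2 they agree before dosing and disagree afterwards. The edit looks like an attempt to align the footer with section 11.2 that left out the time limit. That intent is inferred; Amendment 2 does not state it.

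**Step 2. Are both texts in force?** The changes that Amendment 2 shows in section 11 are to 11.1, 11.5 and 11.6.2, not to 11.2. Amendment 7 (Japan, 2019) reprints from section 11.2 "All AEs, either observed by the investigator or reported by the patient, must be reported by the investigator and evaluated". The conflict is therefore between two current texts, not between old and new.

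**Step 3. Could lost mark-up explain the footer?** Amendment 2's convention is "Any text deleted from the protocol is written using strike through", and strike-through does not survive in the text read from the PDF. The restricting words are absent from version 1.0, so they are an insertion and not surviving deleted text. A time limit, had one been added, would also appear as text, and none does.

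**Step 4. Was it corrected later?** Table 2-2 was reopened for footer 9 (Amendments 3 and 8), footer 12 (Amendment 4) and the body-weight footer (Amendment 5). None of these shows a change to footer 5.

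**Step 5. Size.** Let s be the share of post-dose AEs that a site regards as associated with trial activities. A site following footer 5 alone reports s times its true count, a shortfall of 1 − s. The documents do not give s, so the shortfall at such a site could lie anywhere from 0 to 1. For illustration only:

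- s = 0.9 gives 1 − 0.9 = 10% lost.
- s = 0.5 gives 1 − 0.5 = 50% lost.

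At a site following section 11.2 the shortfall is 0. The number of sites of each kind is unknown, so no trial-level figure can be derived.

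**The case against.** The strongest reply is that the detailed rule is intact and well supported. Section 11.2 still requires all AEs. Parents are asked about AEs at every contact (section 11.2), and the 12-weekly contacts enquire about all AEs (section 8.8.4). Monitors compare medical records with the eCRF for omissions (section 13), and Amendment 2 requires protocol training for investigators (section 21). None of its rationale items mentions narrowing AE collection; the nearest describes a clarification of Table 2-1. SAEs and MESIs have their own forms and deadlines in section 11.2. Harm needs a site to follow one footnote and disregard the full section.

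Much of this stands. A reader might infer that Amendment 2 changed the reporting rule and that the AE endpoint will be undercounted. The documents do not support that: they show a conflict that could lead to omissions, with several safeguards against them. The safeguards do not remove the conflict, however. Asking about events brings them to light but does not settle which text decides whether they are entered.

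A second reply concerns scope. The AE row is reprinted in Amendment 2's change list with no visible change, and deleted text elsewhere in that table shows as live text. For example, footer 19 gives its visit interval in both weeks and EDs. The marker may have been struck from the row label. Amendment 8's reprint of Table 2-1 leaves out the AE row, and consolidated versions 3.0, 4 and 5 are not supplied. This also stands, so the placement needs checking. A marker moved to a single visit would normally show, because other cell markers survive in that table and no AE cell carries a 5. Even without a marker, the footer's own wording starts at consent and has no end.

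**Conclusion.** The conflict is real. As amended, footer 5 omits the consent-to-first-dosing limit and contradicts section 11.2 for post-dose events not associated with trial activities. The consequence is a possible, not a demonstrated, omission of mainly non-serious post-dose AEs from the treatment-emergent summaries. Its size cannot be computed from the documents, and it is zero where sites follow section 11.2.

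Two further inferences should be avoided. A percentage undercount could be produced only by assuming both the share of unassociated AEs and the share of sites using the flow chart, and neither is in the documents. Nor does it follow that missing events would concentrate in the unlikely category of causality: section 11.1 judges causality against the trial product, whereas footer 5 refers to trial activities, which is a different test.

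The conclusion assumes that the text read from the PDF gives footer 5 and its placement correctly, and that the consolidated versions not supplied did not correct it.

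**What to change.** First check the marked-up Amendment 2 or a consolidated protocol for the wording of footer 5 and the position of its marker. If confirmed, reword the footer to match section 11.2, for example: *From informed consent until the first dose of N8-GP, record an AE only when it is linked to a trial-related activity; from the first dose through the EOT visit, record every AE.* Send sites a short clarification.

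The cost is one footnote and one letter, with no new assessment or analysis. A further amendment may no longer be possible: the file carries a clinical trial report appendix date of 24 February 2022, after the planned last visit of 13 November 2021. In that case, describe the discrepancy in the trial report beside the AE tables and state that section 11.2 was the intended rule, if the sponsor can confirm it. A retrospective search for unreported post-dose events is optional. It would cost considerably more and is not part of this low-cost fix.
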